3.3.1 Violation of Study Plan

Participants that do not complete registration for the W-GenZD application or who do not attend a teletherapy group within the first week following randomization will not be removed from the study for failure to access the study intervention. Participants will remain in the study and will continue to receive invitations to complete survey assessments. Depending on randomized condition, those in the CBT-Lite group may attend the remaining sessions (2-4) and those in the W-GenZD group may download the app and program the duration of the 4-week intervention period. All participants randomized to this protocol, regardless of participation or withdrawal status, will be included in the intent-to-treat analysis (see section 9.0).

4. Study Design

This study will be a randomized controlled trial of W-GenZD versus CBT-lite teletherapy groups. The trial will consist of 3 primary phases: Screening/Baseline, Treatment, and a Follow-up period.

All adolescents referred to the CHKD Mental Health Program are provided an orientation about the clinical care program and participate in a brief clinical triage assessment to assess needed level of care. In general, information about the study and consent to contact is included in the welcome packet. As part of recruitment efforts, CHKD may provide families with tokens of engagement (e.g., stress balls). Based on the brief clinical triage assessment, if the adolescent is appropriate for the low-intensity intervention track, study staff will re-introduce the study during the telephone interview and assess the family's (adolescent and parent/guardian) interest in participating. Research staff will follow up with those who expressed interest, present the study, obtain informed consent and assent, facilitate assessment completion, and assess inclusion/exclusion criteria.

Adolescents who do not meet eligibility criteria will be thanked for their interest and willingness to volunteer, and will return to the routine clinical care pathway at CHKD.

Adolescents who meet inclusion criteria after completing the screening and baseline questionnaires will be randomized 1:1 to the treatment groups. Participants who are randomized will enter the 4-week treatment period where they will engage in the assigned group treatment and complete assessments at study day 5, week 2, and at end of treatment, week 4. At week 4, study application access and participation in the teletherapy groups will end and participants will complete a follow-up assessment at the end of study, week 8.

Figure 1. Participant flow through study

4.1 Treatment Arms

4.1.1 W-GenZD Mobile Application

W-GenZD is a mobile application program that delivers evidence-based therapy for the symptoms of mild-moderate depression and anxiety in adolescents in brief "conversations" with a fully automated relational agent called Woebot. It is a brief, self-guided 4-week intervention that draws from CBT, IPT-A and elements of dialectical behavior therapy (DBT), depending on the presenting situation, to help the adolescent develop emotion regulation skills in the context of their everyday life. In this way, the mobile application is designed to be targeted, relevant, and integrated into the lived experience of adolescents, capable of delivering the appropriate technique for the problem at hand, at the time of need. W-GenZD was adapted from and differs from the broader Woebot platform in key ways.

- 1. Unique Check-In Flow
- 2. Unique Onboarding
- 3. Unique Content Modules
 - a. Psychoeducational Lessons: New topics such as Media Literacy and Identity
 - b. Psychotherapeutic Tools: New tools for Communication Analysis and Conversation Role-Play, as well as Relationship Development
 - c. Behavioral Health Problem Areas: expanded Sleep, Communication, Procrastination, Loneliness, and Anxiety areas.

W-GenZD was built from a synthesis of:

- 1. Human-centered design process, to understand the needs and lived experience of adolescents with depression,
- 2. Interviews with clinicians expert in adolescent mental health, which highlighted and underpinned the breadth and nuance in clinical presentation and therapeutic approach, and
- 3. Critical analysis of the literature on current standard of care, effective approaches, modalities, and problems to be solved.

Participants will gain access to the study application once randomized throughout Week 4 (EOT) and are encouraged to use the app for a minimum of 5 minutes per day during the treatment period.

4.1.2 CBT-Lite Teletherapy Groups

The CBT-Light teletherapy groups aim to provide support to adolescents seeking treatment after they have been triaged into CHKD's low-intensity track. In the clinical setting, CHKD offers CBT-lite teletherapy groups for youth with low intensity symptoms who are waiting for individual care, as described above. The research-specific groups are a brief, 4-week intervention held once weekly for an hour, and limited to those participating in this protocol. Enrolled participants randomized to group are offered the group that best fits their schedule. An assigned study clinician will facilitate each teletherapy group with up to 10 adolescents in each session. Each group begins with orientation and reviewing group rules, individual check-ins with each participant (rating stress level and hopefulness), followed by a guided mindfulness moment.

Groups will be conducted on an open-enrollment, rolling topic basis, allowing for participants to join the next available session following randomization and complete all 4 sessions during their study treatment period. Sessions are designed to draw from elements of CBT and the 4 topics include: Building a coping tool box, Accept your feelings, Challenge negative thoughts, and Problem solving. Fidelity to group process is monitored by non-clinician study team member.

Participants randomized to the CBT-Lite TeletherapyGroup will be offered access to the Woebot LIFE app at the end of study.

5. Study Assessments and Procedures

All assessments, and their corresponding administration points, are listed in Table 1.

5.1 Demographic Questions

At screening, basic demographic information including gender and sexual identity, racial background, and level of education will be collected.

5.2 Psychiatric History

Participants' parent/guardian will be asked at screening about their child's history of psychiatric illnesses, specifically those exclusionary to this study, and for any prior or concomitant medications and therapy. Information around current and past year suicidality and substance use will also be collected.

5.3 CHKD Brief Clinical Needs Assessment

If a participant is deemed eligible for the low-intensity CHKD track and consents for this research study, the following data from the CHKD triage and brief-clinical needs assessment will be collected at screening to help establish eligibility:

- Preliminary diagnosis (given presenting problem(s) of depressive or anxiety symptoms)
- Low-intensity track eligibility, by rule out of the following:
 - Suicidal ideation within the last 2 weeks or be a current risk to self/others
 - Psychotic presentation
 - Meets criteria for an eating disorder
 - History of mania
 - Substance use disorder (as the primary clinical problem)
 - Imminent risk of expulsion
 - Currently prescribed 4 or more psychotropic medications

Additional triage and brief-clinical needs assessment data will be collected from CHKD, as it becomes available based on completion by the family, and may include the following:

- Triage assessment scores:
 - Ask Suicide Screening Questions (ASQ)
 - Safe Environment for Every Kid (SEEK) Parent Questionnaire
 - Strengths and Difficulties Questionnaire (both parents/guardian and adolescent)
 - Pediatric Quality of Life (PQL) (both parents/guardian and adolescent)

5.4 Clinical Outcomes

The following clinical outcomes will be collected via survey platform by adolescent self-report.

The Patient Health Questionnaire (PHQ-8)

The 8-item PHQ, an abbreviated version of the PHQ-9, the PHQ-8, will be used to assess mood and anxiety symptoms respectively. The PHQ-9 is a widely used self-report measure, with demonstrated reliability and sensitivity to clinical *CONFIDENTIAL* 20

change. The PHQ-8 excludes an item assessing suicidality [34].

Generalized Anxiety Disorder (GAD-7)

The GAD-7 item scale is a brief self-report tool to assess the frequency and severity of anxious thoughts and behaviors over the past 2 weeks. It is a widely utilized, reliable, and valid measure of anxiety [35].

Mood and Feelings Questionnaire (MFQ)

The MFQ short-version is a child self-report assessment consisting of a series of 13 descriptive phrases related to the participant's recent feelings and behaviors. Respondents reflect on whether the phrases are "true", "sometimes true", or "not true" of the subject's feelings and behaviors during the past two-week period [36].

5.5 Working Alliance

Working Alliance Inventory (WAI-SR)

The WAI-SR is a measure of therapeutic bond and consists of a composite score and three subscales; Bond, Goal, and Task. Bond measures the strength of the therapeutic relationship between the client and therapist. Goal measures agreement on the goal of the overall therapeutic program between the client and therapist. Task measures agreement between the client and therapist, regarding the specific activities needed for a therapeutic change to occur such as doing an exercise to ameliorate a specific symptom [37]. The present study utilized the validated 12-item Short Revised version (WAI-SR) with minor changes to language, replacing "therapist" with the name of the assigned treatment group.

5.6 Acceptability and Feasibility

The Client Satisfaction Questionnaire (CSQ-8)

The CSQ-8 is an 8-item measure used to assess client's satisfaction with treatment on a 4-point scale (1 = "very dissatisfied" to 4 = "very satisfied"). Example questions include, "how would you rate the quality of service you received?" and "did you get the kind of service you wanted?" Total sums range from 8-32, with high scores indicating greater satisfaction with W-GenZD. The CSQ-8 has been widely disseminated and considered both valid and reliable (α ranges = .83-.93) [38].

Satisfaction Questionnaire

Participants will be asked 3 open-ended questions about what they found most helpful about their treatment arm, what would make it better, and if there is any other feedback they would like to share.

Usage Rating Profile Intervention (URPI)

URPI-Feasibility and URPI-Acceptability are both 6-item subscales from the URP-Intervention Revised (URP-IR) scale. Responses range from 1 = "slightly disagree" to 6 = "strongly agree". Scores are averages, with greater scores indicating greater intervention feasibility or acceptability. The URPI-Feasibility inquires about factors that impact treatment usage (i.e., intervention quality) and has acceptable reliability, internal consistency, and discriminant validity. The URPI-Acceptability inquires about intervention acceptability. It has demonstrated high reliability and internal consistency [39].

Safety Procedures

Utilization data, including frequency, type, and outcomes, will be collected throughout this protocol to report on incidents of Safety Net Protocol triggers and the occurrence and relatedness of AE/SAEs.

App Engagement

Data characterizing mobile application use, including days in app and content engagement, will be collected throughout treatment (4-weeks) for participants randomized to the W-GenZD treatment arm.

Group Attendance

Group attendance will be kept by facilitators/study coordinator throughout the study and provided through the EDC from randomization through the end of treatment (4-weeks) for those randomized to the CBT-lite teletherapy treatment arm.

Healthcare Utilization

Data regarding a participant's healthcare resource utilization (HCRU), social determinants of health and comorbidity data will be collected throughout the pre-study, treatment and follow-up periods. Participants will have various lengths of engagement within the CHKD system, therefore pre-study HCRU data will be collected from the time of first engagement through entering the study and until end of study. This will include CPT and ICD codes, diagnoses (e.g., EHR Problem List data), treatments including medications related to pediatric visits in the CHKD system, (emergency department visits, pediatric and mental health care office visits, outpatient behavioral health care visits, and medications available for services provided in the CHKD health system) and any relevant lifetime psychiatric assessments (e.g., Vanderbilt, PHQ).

5.7 Parental Check-Ins

At weeks 2, 4, 6, and 8 a study personnel will conduct a telephonic visit with the participant's parent/guardian. During these calls information regarding AE/SAEs and concomitant medications will be collected. These calls will also serve as an opportunity to address any trouble-shooting around the use of the application or attendance to the CBT-lite teletherapy group. See Appendix 1. for full guidelines for these check-ins.

5.8 Unscheduled Telephone Visit: Safety Response

If at any time following consent, through the end of study, that an adolescent has a safety event, defined as a risk or actual harm to self or others, qualified study personnel will conduct an immediate unscheduled protocol visit (telephone contact). Study personnel will learn of these events through several methods:

- 1. A participant in the Gen-ZD treatment group confirms a crisis in the mobile app (See Section 6.)
- 2. A CBT-lite teletherapy group facilitator learns of risk during group session
- 3. Is contacted directly by a participant or parent/guardian

During the unscheduled telephone visit, the clinician will assess suicidality, thoughts of self-harm or harm to others, including plan and intent, as well as protective measures and a safety plan. For the full SNP Response procedures and guidelines, refer to Appendix 2.

5.9 Participant and Parent/Guardian Exit Interview

The goal of the post-study interviews is to identify opportunities for product improvement. This includes discussion of the participant's mental health journey & typical concerns, as well as their experience with the product. During study consent, participants will be presented with the opportunity to consent to this optional study procedure. Following study completion at 8-weeks, if consent was granted to be contacted for an exit interview, a study representative will reach out and schedule with participants based on availability. Efforts will be made to interview participants equally from both treatment arms of the study. Due to availability of interview appointments and potential number of interested participants, not all who express interest in this optional procedure will be contacted.

6. Safety Net Protocol (SNP)

Woebot's (W-GenZD) natural language processing algorithm was designed to detect language that suggests a user may be in imminent crisis. Specifically, it will detect if a user inputs, via free response text entry, a phrase or word(s) that matches an a-priori determined and thorough list of such phrases and word(s) that may be used in imminent crisis situations. After the algorithm detects these words, it will inquire if it is indeed a crisis situation. If the user says yes, the application will notify the participant that the on-call study clinician will be reaching out to provide support and assess safety.

After notification of the safety response follow-up, W-GenZD will offer to help that person in the moment with their upsetting thoughts. This is clinically relevant because suicidal thoughts are thoughts that can be addressed through cognitive therapy techniques. Our value herein is to support and provide in-vivo skills to someone who seeks assistance in changing their emotions and thoughts in the moment.

Once a crisis has been confirmed, W-GenZD will send a HIPAA compliant alert (via Jabber, Spok, or other mutually agreed upon communications channel) to designated clinical staff who will be on call to provide 24/7 coverage of these alert messages. This individual, who will be on the study team, will be embedded in the CHKD system of care, and therefore in a position to triage the individual, engage directly with the participant to ensure their safety and wellbeing, and/or refer to emergency services as necessary. Triage decisions resulting from the clinical alerts will be separately logged, in HIPAA complaint fashion, for purposes of improving the Safety Net Protocol.

7. Concomitant Medication and Therapy

While many adolescents who are seeking services may not be prescribed psychotropic medications, those that are connected to treatment will be allowed to participate in this study and continue their current regimen if the following inclusion/exclusion criteria is met:

- If currently prescribed antidepressant medications (e.g. escitalopram/Lexapro, fluoxetine/ Prozac), antipsychotic medications (e.g. aripiprazole, asenapine, olanzapine, paliperidone, quetiapine, risperidone), or stimulants (e.g. amphetamine/Adderall, Methylphenidate/Ritalin) and alpha agonists (e.g. atomoxetine/Strattera, Guanfacine/Intuniv), they are at a regular, stable dose for at least 60 days at screening with no plans to change medication/dose throughout the study
- 2. Is not currently using benzodiazepines (e.g. lorazepam, clonazepam, alprazolam, diazepam, triazolam) or certain sleep aids (zolpidem, eszopiclone, zaleplon)

Use of concomitant medications throughout the study will be collected at baseline, week 4 EOT and week 8 EOS.

8. Risk and Benefit Assessment

8.1 Risks

Given that the research aims to enroll participants into a low-risk intervention that replaces a passive waitlist, we do not anticipate that participation in the study will be associated with elevated risk. Participation in the study is independent to pharmacological treatments being utilized by participants and we do not anticipate that participation in the study will impact pharmacological treatments. The overall evaluation of risk is that it is low.

8.1.1 Misunderstanding the Capabilities of the Application

W-GenZD is not intended to be a crisis service, however given the nature of the targeted population and experience of depression, there is the potential participants may misunderstand the limitations of the app. To

Woebot Health W-GenZD-003

mitigate this risk, the study will provide clear information on the capabilities of the app, intended use, and limitations of the SOS feature at consent/assent, randomization, and key points throughout. Additionally, when a safety event is triggered, an on-call CHKD clinician will receive an immediate notification and follow-up with the participant as outlined in the Safety Net Protocol.

8.1.2 Data Breach

All study data, from participant self-report and CHKD study personnel, are gathered on either a HIPAA-compliant web platform that resides behind Woebot Health security firewalls or via a HIPAA-compliant survey platform, thus actual risk from data breach for study data is low. Research material obtained from human subjects will involve behavioral and psychological assessments including self-report questionnaires. All data obtained via Woebot will be encrypted and stored on Amazon Web Services (AWS) and/or Google Cloud Platform; Woebot Health data gathering and storage procedures are compliant with both HIPAA and the European Union's General Data Protection Regulation. Only members of the research team will have access to identifiable study data. De-identified data will be accessible to the product development team (designers, user researchers, and product managers) as well as the research team.

8.1.3 Potential Upset due to Study Procedures

Foreseeable risks to participants include the possibility that some assessment questions and/or treatment procedures may be upsetting to participants. Experience with similar populations has indicated that the risk of emotional upset during the assessments is low and if it occurred, the upset would likely be temporary and not be serious in nature. Such risks will be minimized by the thoughtful selection of questionnaires. Participants will also be informed that they may withdraw from the study at any time and if requested, appropriate resources will be provided.

There is also a potential risk of distress at the end of the assigned study intervention(s). Participants are informed during the consent process, and are reminded at randomization, parental check-ins at weeks 2 and 4, and at the end of the surveys at week 4 that they will no longer have access to the study intervention(s) after week 4. Return to care and other resources are provided at week 6 and the end of the study at week 8 or earlier if deemed necessary by clinician assessment.

Participants can refuse and withdraw from participation at any time. If they withdraw consent from the study, they will no longer have access to the study treatments.

8.2 Benefits

When evaluating the risks and benefits of the proposed study, it is believed that risks are relatively minimal when compared to the potential therapeutic benefits that subjects are likely to receive. The possible benefits of receiving Woebot or participating in the CBT-lite teletherapy groups include potentially improving mood (anxiety, stress, and/or depression), acquiring practical psychotherapeutic skills (from cognitive behavioral therapy, dialectical behavior therapy, and mindfulness), and receiving psychoeducation about mental health.

Participants who improve mood may derive additional benefits should said mood improvements be associated with other psychological improvements such as interpersonal or occupational functioning. Study of the effectiveness of the W-GenZD intervention will also benefit society more generally by providing data on the efficacy of Woebot.

9. Statistical Analysis

This study was designed to assess the feasibility of delivering W-GenZD as an option for adolescents ages 13-17 years triaged into a low intensity track for mental healthcare while on a waiting list for definitive treatment.

Primary Aim: What is the feasibility and acceptability of the W-GenZD among a group of adolescents and who have been screened and triaged into low-intensity treatment within CHKD?

Hypothesis: W-GenZD will be acceptable and feasible.

Primary Endpoints: Feasibility and acceptability metrics including:

- Study enrollment rates
- URPI -Feasibility; UPRI Acceptability {12 items}
- Client Satisfaction Questionnaire (CSQ-8) {8 items}
- App engagement metrics {Woebot condition}
 - *Measure*: App engagement, including number of messages sent to Woebot by week and number of days active in the app by week
 - *Measure:* Content and program satisfaction ratings, including data collected in app (e.g., module ratings)

Analysis Plan:

Statistical analysis will be descriptive. Continuous variables will be summarized using tables of descriptive statistics: number of participants with recorded observations, mean, standard deviation, median, first quartile, third quartile, minimum, maximum and interquartile range (IQR). Study enrollment rates will be reported. For subjects in the Woebot condition the app engagement measures will be summarized. Similarly, the content and program satisfaction ratings, including data collected in the app will be summarized. Categorical and ordinal variables will be described using frequencies and percentages. The amount of missing data will be summarized by treatment condition.

Secondary Aim: What is the preliminary comparative efficacy of W-GenZD and CBT-lite telehealth zoom groups to manage mood and anxiety concerns?

Hypothesis: W-GenZD will be non-inferior to CBT-lite with regards to the secondary endpoints at 4-weeks end-of-treatment

Secondary Endpoints:

• PHQ-8

Analysis Plan:

To assess the secondary aim non-inferiority tests will be used. The secondary analysis will focus on meeting the secondary aim of an initial test of the non-inferiority of W-GenZD as compared to CBT-lite telehealth zoom, to manage mood concerns. An intent-to-treat analysis will be used with participants analyzed as assigned to the treatment conditions. Mean, standard deviation, median, first quartile, third quartile, minimum, maximum and interquartile range (IQR) will be reported for each variable at each time point. A non-inferior test will be employed. The margin of clinical significance for the outcomes will be set to 2. These tests will be performed for each variable using the end of treatment time point. In addition, a meta-analysis will be performed to assess the active control effect of the cbt-based telehealth in a pediatric population. Full details will be specified in the SAP.

Tertiary Aim: Investigate potential between group differences..

Tertiary Endpoints:

- Working Alliance Inventory-SR (WAI-SR)
- GAD-7
- MFQ

Analysis Plan:

The tertiary analysis will focus on meeting the tertiary aim of an initial test of the potential between group differences on the WAI-SR, GAD-7, and MFQ. An intent-to-treat analysis will be used with participants analyzed as assigned to treatment conditions.

Woebot Health W-GenZD-003

Exploratory Aim: To observe and describe upon the utilization and outcomes of the safety procedures utilized within this study (Safety Net Protocol, AE/SAEs and device relatedness). For each AE/SAE type, and Safety Net Protocol, *n* will be reported. To explore healthcare utilization, social determinants of health, and comorbidity data for pre-study and during-study (treatment and follow-up) periods.

Exploratory Endpoints:

- Safety Net Protocol, AE/SAEs and device relatedness
- Pre-period and study-period healthcare utilization data. This will include:
 - Diagnosis (e.g., ICD code) and service rendered (e.g., CPT code)
 - Emergency Department utilization
 - Primary care utilization (e.g., primary care well visit and sick visit appointment)
 - Behavioral-health related utilization (psychiatry, psychology, other therapist, etc)
 - Psychiatric medication prescriptions
 - Social determinants of health information (e.g., food and housing insecurity and social work utilization)
 - Comorbidity data (i.e., any additional behavioral health or physical health diagnoses)
 - Problem List
 - Any relevant lifetime psychiatric assessments (e.g, Vanderbilt, PHQ)

Analysis Plan: Primary care utilization, behavioral health care visits utilization, psychiatric medication utilization, Emergency Department visits utilization, social determinants of health, comorbidity and diagnoses data, and psychiatric screenings where relevant will be summarized using descriptive statistics for W-GenZD and CBT-lite telehealth zoom groups.

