10.2.2 Causality Rating	26
10.2.3 Severity of ADE	26
10.3 Reporting	26
11. Study Key Personnel	26
CHKD Principal Investigator: [name] [name]., FAAP	26
Woebot Liaison: [name].	27
Woebot Liaison: [name].	27
CHKD Sub-Investigator: [name], D.O.	27
CHKD Co-Investigator: [name]. CONFIDENTIAL	27 5

Woebot Health	Version 5.0
W-GenZD-003	31 May 2023
References	28
Appendix 1. Parental Check-In Guidance	31
Appendix 2. Unscheduled Telephone Visit: Safety Response Follow-Up	32

Version 5.0 31 May 2023

Table 1. Schedule of Events

	Screenin	ng Period		Treatment Per	iod	Follow	v-Up Period
Visit Weeks/Days	Screening Day -7 to -1	Baseline Day 0	Visit 2 Day 5 (+2)	Visit 3/Week 2 Day 14(+6)	Visit 4/ Week 4 (EOT) Day 28 (+6)	Visit 5/ Week 6 Day 42 (+6)	Visit 6 Week 8 (EOS) Day 56 (+6)
		_					
Informed Consent/Assent	Х						
Demographics ^{c, d}	Х						
Psychiatric History ^{c, d}	Х						
Prior & Concomitant Medications/Therapy ^d	Х				Х		
CHKD Brief Clinical Needs Assessment Information ^d	Х						
Eligibility Confirmation (Inclusion/Exclusion)	Х						
Randomization		Х					
Download Study Application ^a		х					
PHQ-8 ^b		Х		Х	Х		Х
GAD-7 ^b		Х			Х		Х
MFQ ^b		Х			Х		Х
WAI-SR ^b			Х		Х		
CSQ-8 ^b					Х		
Satisfaction Questionnaire ^a					Х		
UPRI ^b					Х		
App Engagement Metrics (W-GenZD only)					Х		
Weekly teletherapy Group Attendance (CBT-lite				v			
only) ^d				^			
Parental Check-Ins (Telephonic)				х	х	х	Х
SNP/Safety Response ^e				Х			
Healthcare Utilization ^{c, d}							Х
Assessment of AE/SAEs				Х	Х	Х	Х
Termination of W-GenZD and Teletherapy Access					Х		
Participant and Parent/Guardian Exit Interviews ^f							X

Woebot Health W-GenZD-003 Version 5.0 31 May 2023

^a W-GenZD participants only, ^bSelf-Report Clinical Assessment (adolescent), ^c Parent/Guardian Questionnaire, ^dCollected from CHKD system, ^e A SNP or Safety event will trigger an unscheduled visit from ICF to EOS, see section 5.6, ^fOptional study procedure; EOS = End of Study; EOT = End of Treatment; SNP=Safety Net Protocol

Protocol Synopsis

Study Device	W-GenZD		
Protocol Number:	W-GenZD-003		
Protocol Title:	A Randomized Controlled Trial of the Feasibility and Acceptability of W-GenZD versus CBT-lite teletherapy for Adolescents seeking Mental Health Services		

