Treatment Regimen:	W-GenZD: 5-10 minutes of daily use recommended Teletherapy CBT Groups: 1 group/week of treatment period		
Duration of Study Participation:	8 weeks		
Number of Participants:	260 participants		
Number of Sites:	1		
Primary Endpoints:	 Primary Feasibility and Acceptability outcomes at 4-weeks: Usage Rating Profile Intervention (URPI)-Feasibility and URPI-Acceptability Client Satisfaction Questionnaire (CSQ-8) 		
	Additional feasibility and acceptability metrics:		

	 App engagement metrics (W-GenZD condition) Content/Program satisfaction ratings (both conditions) Group attendance (CBT-lite teletherapy condition) Qualitative findings about the participant experience, based on interviews with a self-selected subset of participants (adolescent and parent/guardian)
Secondary Endpoints:	 Patient Health Questionnaire for Teens (PHQ-8) total score Generalized Anxiety Disorder Questionnaire (GAD-7) Mood and Feeling Questionnaire (MFQ)
Tertiary Endpoint:	• Working Alliance Inventory-SR (WAI-SR)
Exploratory Endpoints:	 To observe and describe the utilization and outcomes of the safety procedures utilized within this study (Safety Net Protocol, AE/SAEs and device relatedness) Pre-period and study-period healthcare utilization data. This will include: Diagnosis (e.g., ICD code) and service rendered (e.g., CPT code) Emergency Department utilization Primary care utilization (e.g., primary care well visit and sick visit appointment) Behavioral-health related utilization (psychiatry, psychology, other therapist, etc) Psychiatric medication prescriptions Social determinants of health information (e.g., food and housing insecurity and social work utilization) Comorbidity data (i.e., any additional behavioral health or physical health diagnoses) Problem List Any relevant lifetime psychiatric assessments (e.g., Vanderbilt, PHQ)
Interim Report:	Readout of complete baseline sample descriptive stats (demographics, enrollment data, etc) and baseline scores of measures

1. Introduction

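### The primary hypothesis of feasibility and acceptability has no criterion, and the plan gives no interval or between-arm difference for URPI and CSQ-8

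*Combined protocol and SAP*

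**What the plan says.** Section 9, Primary Aim, gives the hypothesis as "Hypothesis: W-GenZD will be acceptable and feasible". The analysis plan beneath it opens with "Statistical analysis will be descriptive" and lists counts, means, standard deviations, quantiles, ranges and frequencies. The only item it promises by treatment condition is the amount of missing data.

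The Synopsis and Section 2 use the label "Primary Feasibility and Acceptability outcomes at 4-weeks" for the two URPI subscales and CSQ-8. They place app engagement, satisfaction ratings and group attendance in a second tier of additional metrics. Section 9 merges the tiers into one list of primary endpoints, which begins with "Study enrollment rates" and also contains app engagement.

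Section 5.6 defines the scales but sets no cut-off. For URPI: "Scores are averages, with greater scores indicating greater intervention feasibility or acceptability". For CSQ-8: "Total sums range from 8-32, with high scores indicating greater satisfaction with W-GenZD". The Table 1 footnotes read "a W-GenZD participants only, ^bSelf-Report Clinical Assessment (adolescent), ^c Parent/Guardian Questionnaire"; CSQ-8 and URPI carry footnote b, not footnote a, and are scheduled at Week 4.

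Elsewhere in Section 9, PHQ-8 gets a non-inferiority test with a margin of 2, and WAI-SR, GAD-7 and MFQ get a between-group test. The one deferral of detail to an SAP is in the secondary-aim plan.

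**The concern.** A hypothesis needs a result that would count against it. Here any Week 4 mean on URPI or CSQ-8 could be reported as support, because the plan does not say what level is acceptable or feasible.

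The second issue is distinct. The trial title frames feasibility and acceptability as W-GenZD versus CBT-lite, and participants are randomised 1:1. Between-arm inference is nevertheless planned only for the secondary and tertiary scales. The primary scales get neither a difference nor any measure of precision, so the report need not say how W-GenZD compares with CBT-lite on them, or how firmly.

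Merging the two tiers in Section 9 adds to the first problem: with several metrics of equal rank and no criterion, emphasis can be chosen after the data are seen.

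**Working it through.** **No planned figure to reproduce.** The documents give no precision or power statement for the primary aim. Section 3.1 gives a minimum of 260 participants, about 130 per arm, without alpha, power, SD or dropout. The check is therefore what that number would deliver on the primary scales.

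**Are the scales collected in both arms?** In Table 1 footnote a marks W-GenZD-only items, and CSQ-8 and URPI do not carry it. This supports collection in both arms, but it is an inference. Section 5.6 describes CSQ-8 scores as satisfaction with W-GenZD. The footnotes are also not fully reliable: Table 1 marks the Satisfaction Questionnaire as W-GenZD only, while Section 5.6 has it ask about the participant's own arm, and the Synopsis and Section 2 list satisfaction ratings for both conditions.

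**Inputs**
- n = 130 per arm (Section 3.1); n = 104 per arm if 20% are lost (assumed; 130 × 0.8).
- SD: not in the documents. Assumed 0.8 to 1.2 for URPI (scored 1 to 6) and 4 to 6 for CSQ-8 (scored 8 to 32).
- CBT-lite groups of up to 10 (Section 4.1.2); ICC 0.05 (assumed).

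**Independent observations.** Half-width of the 95% interval for the difference = 1.96 × SD × √(2/n).
- n = 130: 1.96 × √(2/130) = 0.243 SD
- n = 104: 1.96 × √(2/104) = 0.272 SD

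For a single arm mean, 1.96 × SD/√n gives 0.172 SD at 130 and 0.192 SD at 104.

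**Clustering in CBT-lite only.** Design effect in that arm = 1 + (10 − 1) × 0.05 = 1.45. The variance of the difference changes from 2/n to (1 + 1.45)/n, a ratio of 2.45/2 = 1.225. The half-width grows by √1.225 = 1.107, about 11%.

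| Half-width of difference | 130 per arm, independent | 130, clustered | 104 per arm, independent | 104, clustered |
|---|---|---|---|---|
| SD units | 0.24 | 0.27 | 0.27 | 0.30 |
| URPI, SD 0.8–1.2 | 0.19–0.29 | 0.22–0.32 | 0.22–0.33 | 0.24–0.36 |
| CSQ-8, SD 4–6 | 0.97–1.46 | 1.08–1.61 | 1.09–1.63 | 1.20–1.80 |

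The clustered columns keep groups at 10, the stated maximum; smaller groups would reduce the inflation at the same ICC.

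**The case against.** The strongest reply is that a feasibility trial may properly be descriptive, and that the primary aim asks about W-GenZD alone. Comparison is assigned to the secondary and tertiary aims, so leaving it out of the primary aim is a design choice. Much of this stands: no primary significance test is needed, and describing the aim as estimation is a legitimate answer. It does not explain why a hypothesis is stated with nothing to judge it by, or why the estimates come without intervals in a trial titled as a comparison.

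Several stronger readings are tempting and should be resisted:
- A reader might infer that the hypothesis is irrefutable because the arms are not compared. It is an absolute claim about W-GenZD. A difference alone would not refute it, since both arms could score well or badly; the missing criterion is the cause.
- A reader might infer that Section 9 newly brings app engagement under the primary heading. The Synopsis and Section 2 already list it there, as an additional metric. Section 9 drops the ranking, and only enrolment rates are new.
- A reader might infer that W-GenZD is meant to replace the groups. Section 1.3 calls it a viable option, Section 8.1 speaks of replacing a passive waitlist, and non-inferiority is hypothesised for PHQ-8 only.
- A reader might infer that nothing comparative could ever be learned. If means, SDs and counts are tabulated by arm, a difference and an unadjusted interval can be derived. The plan does not promise that table.

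The precision figures also have limits. The SDs, loss and ICC are assumed. Section 3.3.1 keeps participants who never start treatment in the study, so missing Week 4 ratings may not be random.

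**Conclusion.** The point holds in two parts. First, the primary hypothesis has no criterion anywhere in the text provided, and the only deferral to an SAP concerns the secondary aim, so no result could count against it. Second, the randomised comparison that the title implies is not planned for URPI and CSQ-8, and no interval is planned for either arm.

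Precision is not a reason for the omission. The difference would be known to within about 0.24 SD with 130 per arm, 0.27 SD after an assumed 20% loss, and about 11% wider under the assumed clustering. This is worth correcting because the change is cheap. It does not show that the trial is invalid or that a descriptive primary analysis is wrong in itself. The comparative part rests on both arms completing the scales, which Table 1 indicates and the CSQ-8 wording in Section 5.6 leaves unclear.

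**What to change.** In Section 9:
1. Keep URPI-Feasibility, URPI-Acceptability and CSQ-8 at Week 4 as the primary set. List app engagement as an additional metric, as the Synopsis and Section 2 do, and add enrolment rates to that tier.
2. For each primary scale, report the mean by arm with a 95% confidence interval and the W-GenZD minus CBT-lite difference with a 95% confidence interval, as estimation. Allow for clustering by teletherapy group in the CBT-lite arm.
3. Describe the primary aim as estimation, unless a benchmark for the W-GenZD mean is fixed before any Week 4 outcome data are examined.

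In Section 5.6, align the CSQ-8 wording with Table 1 so that it covers both arms.

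The cost is wording and three extra contrasts, with no added visits or participants if both arms complete the scales as Table 1 indicates. The downside for the sponsor is that an unfavourable or wide interval would be visible in the report.
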